randomized to either the education toolkit intervention condition or treatment-as-usual control condition in a 2:1 ratio. For participants in the control group (Aim 2 and those randomized to control group in Aim 3), there will be no change to the nature of provider communication with families about closed head injury/concussion. Data will be collected about the experience that family's have seeking care in the ED for their child's closed head injury. For both Aims 2 and 3, survey data will be collected from parents at three time points: at initial ED visit before discharge, one day post-visit, and at 2-week follow-up. As part of parent data collection for Aims 2 and 3, all parents will complete the 3-item Brief Health Literacy Screen at the first time point of survey data collection. Please see timeline (uploaded in "Other Attachments" for more information regarding the timing of Aims 2 and 3.

For Aim 3 participants randomized to the intervention group, the parent education toolkit finalized in Aim 1 will be delivered by the study team. Based on feedback from qualitative interviews in Aim 1, the toolkit will consist of brief education from a member of the ED study team at enrollment, followed by asynchronous phone-based follow-up (audio/ voice and/or text). Parents will receive automated daily educational messages related to how they can provide recovery support to their children during the 2-week study period. Automated messages will be delivered via Twilio, by turning on the "initiate survey as SMS conversation" feature in REDCap. Parents will also receive reminders to schedule a follow-up appointment, with an option to receive tailored support from research staff to help with scheduling. A more detailed description and content of each toolkit component can be found in "Aim 3 Parent Education Toolkit Content" uploaded in "Other Attachments".

All patient materials will be available in both English and Spanish. Certified translations will be uploaded prior to use.

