For both Aims 2 and 3, survey data will be collected from parents at three time points: immediately post-visit, one day post-visit, and at 2-week follow-up. A purposive subset of parents who complete all three surveys in Aim 3 will be invited to participate in optional one-on-one qualitative interviews. Interviews will be conducted remotely (e.g., by phone or video conferencing) and will be recorded. As part of parent data collection for Aims 2 and 3, all parents will complete the 3-item Brief Health Literacy Screen at the first time point of survey data collection.

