**Aims 2 and 3: Primary outcomes.** We will compare parenting behaviors (emotional support and instrumental support) at Time 3 between the two groups using chi-squared tests for each behavior and total proportion of behaviors. **Secondary outcomes.** For each group (control and intervention), the percentage of parents reporting receipt of specific discharge components will be calculated and compared. We will also compare rates across specific subgroups, including high vs. low health literacy parents and between parents who speak English at home vs. those who do not. These percentages will be compared across subgroups using chi-squared tests to assess statistical significance. We will also compare characteristics of subjects who (a) agree to participate vs. those who do not, and (b) participate throughout follow-up vs. any lost to follow-up. We will also conduct exploratory analyses of the mean change in parent cognitions related to concussion management (concussion management knowledge, parental anxiety, and behavioral self-efficacy) and child well-being scores (child PEDs-QL and PCSI) from Time 1 to Time 3, between the groups using t-tests, and plotting trajectories for each group. We will adjust analyses for child age, sex, baseline post-concussion symptoms/severity, as well as covariates not determined to be effect modifiers, if associated with outcome and distributions vary by treatment group. Missing data will be examined for patterns with covariates, sensitivity analyses used to assess impact of missing data on results and imputation used as appropriate to address missingness. **Parent experiences with enhanced education.** Survey data will be analyzed descriptively, with associations by insurance status, language, and gender assessed. For qualitative data, audio-recorded and transcribed interviews will be coded using a deductive content analytic approach using consensual qualitative research methods. First, two independent coders will review each interview transcript, applying codes from the CFIR, Communication Accommodation Theory, and USE-EBPI while remaining open to other emergent themes. They will then compare codes and agree on final codes using a process of deliberation and consensus.

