**20.2.** Where the consent process will take place:

**Aim 1:** This will occur remotely (e.g., over the phone or via video conferencing) or in person at a private location (e.g., community library, SCH conference room) as preferred by the participant.

**Aim 2 and 3:** The consent process will take place in or near the SCH emergency department or Urgent Care.

**Aim 4:** (1) Cognitive interviews: An information sheet describing the study will be shared with parents in the SCH Emergency Department or Urgent Care; (2) Online surveys: Participants will review an information sheet about the study online before clicking on to complete the survey.

**20.3.** Steps that will be taken to protect prospective subjects' privacy interests:

**Aims 1, 2, 3, and 4:** Before any research procedures begin, the Research Assistant will explain that participants may choose to skip any questions they do not want to answer and they may discontinue the research study at any time. Research procedures will be conducted in English or Spanish, depending on the participants' preferences.

**20.4.** Waiting period available between approaching a prospective subject and obtaining consent:

**Aims 1, 2, 3, and 4:** There is no waiting period between consent and research procedures; consent/assent/permission will be obtained immediately prior to conducting research procedures.

**20.5.** Process to ensure ongoing consent:

If any new information arises that (1) may be relevant to the participant's willingness to continue participation, (2) affects the rights, safety, and well-being of study subjects, and/or (3) has an impact on study conduct and outcomes, the research team will update enrolled participants that are impacted by any of the above and give them the opportunity to withdraw their consent given previously.

**20.6.** If this box is checked, "SOP: Informed Consent Process for Research (HRP-090)" will be followed:

**20.7.** If "SOP: Informed Consent Process for Research (HRP-090)" will not be followed, address the following:

**20.7.1.** Role of the individuals listed in the application as being involved in the consent process:

Click here to enter text.

**20.7.2.** Time that will be devoted to the consent discussion:

[Click here to enter text.](#)

**20.7.3.** Steps that will be taken to minimize the possibility of coercion or undue influence:

[Click here to enter text.](#)

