 If your population will differ from the representative population where the study will take place (e.g., race, ethnic group, or gender), provide a rationale for the differences.

 If you check a box below, be sure to include the additional safeguards associated with the population.

 Refer to HRP-416 CHECKLIST: Children.

 If the study is minimal risk, explain why. Must also include, as applicable: (1) why direct benefits are anticipated, (2) why risks are justified by anticipated benefit and/or the relationship between risk and prospective benefit compared to available alternatives, (3) why risk represents only minor increase over minimal risk, (4) how study procedures are reasonably commensurate with those inherent to the child's actual or expected conditions, (5) whether the interventions/procedures are likely to yield generalizable knowledge about the participant's condition and why it is of "vital importance" to understanding or amelioration of the participant's underlying disorder or condition, and (6) an explanation of what alternative methods/approaches were considered to make the above assessments (as applicable).

 This population may be wards of the state or any other agency, institution, or entity. Refer to HRP-416 CHECKLIST: Children, Section 6, for additional guidance on required considerations for this population.

 This refers to both cognitive impairments and adults who are incapacitated for any other reason. As applicable, refer to HRP-417 CHECKLIST: Cognitively Impaired Adults.

 Refer to HRP-413 CHECKLIST: Neonates and HRP-414 CHECKLIST: Neonates of Uncertain Viability.

 Refer to HRP-412 CHECKLIST: Pregnant Women.

 Refer to HRP-415 CHECKLIST: Prisoners

 Indicate how you will ensure that there is no coercion or undue influence

 A subject is considered "enrolled" when they consent to be in the study.

 Only applicable for multisite studies.

 i.e., numbers of subjects excluding screen failures.

 Payment for participation is not considered a benefit.

 For example, data will be double entered, data will be reviewed by another study team member to ensure accuracy, etc.

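### The first survey is timed in two ways and never ordered against the toolkit education, so the exploratory Time 1 to Time 3 change comparison may subtract part of the effect it is meant to estimate

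*Combined protocol and SAP*

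**What the plan says.** Section 5.2 gives the survey schedule for Aims 2 and 3 twice. One paragraph reads "survey data will be collected from parents at three time points: at initial ED visit before discharge, one day post-visit"; sections 5.3 and 5.4 agree with it. A later paragraph of 5.2 reads "survey data will be collected from parents at three time points: immediately post-visit, one day post-visit, and at 2-week follow-up". Both are current text.

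For Aim 3 intervention families, 5.2 says that "the toolkit will consist of brief education from a member of the ED study team at enrollment", followed by daily automated messages over the two weeks. Sections 19.1 and 20.1 put consent before randomization. Section 20.4 says "There is no waiting period between consent and research procedures". Section 5.2 refers to an attached timeline "for more information regarding the timing of Aims 2 and 3" and to an attachment with the toolkit content. Neither is part of the text.

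Section 14.1 compares mean change in knowledge, parental anxiety, self-efficacy, PedsQL and PCSI "from Time 1 to Time 3, between the groups using t-tests, and plotting trajectories for each group", and labels this exploratory. The planned covariates are child age, sex and baseline symptoms or severity, plus others that are related to outcome and unevenly distributed between groups. The primary outcome, parenting behaviors, is compared at Time 3 only.

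**The concern.** A change score needs a starting value that the intervention has not touched. Knowledge and self-efficacy are the measures that a short teaching session could move at once, and they lie closest to the hypothesis in section 1.2 that toolkit families will understand more and be better prepared. If parents were taught first and surveyed second, a gain that appeared in the ED and lasted two weeks would show little or no difference in change, and a working toolkit could look ineffective on these measures. For anxiety the distortion could go in either direction. PedsQL and PCSI should hardly be affected, since a conversation with the parent is unlikely to alter the child's condition within minutes.

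**Working it through.** **1. What each section fixes.**

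| Section | What it fixes | Survey against education |
|---|---|---|
| 5.2 (first schedule), 5.3, 5.4 | Survey in the ED, before discharge | Same window as the education; no order |
| 5.2 (second schedule) | Survey right after the visit | Conflicts with the row above; no stated order |
| 5.2 (toolkit) | Education at enrollment | Survey not mentioned |
| 19.1, 20.1 | Consent, then randomization | Survey not placed |
| 20.4 | Consent immediately before research procedures | Survey and education are both research procedures; either may be first |
| 19.2 | First activities by phone, in or near the ED or Urgent Care | Place and mode only |
| 14.1 | Uses the word baseline for symptoms or severity | Suggests intent; fixes no order |

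**2. What is estimated if education came first.** Let e1 and e3 be the group differences at Time 1 and Time 3, with equal SDs and correlation r between the two times.

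- Change score: e3 − e1
- Time 3 adjusted for Time 1: e3 − r × e1
- Time 3 alone: e3

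Only the last is free of the early effect. For e3 = 0.3 SD and e1 = 0.15 SD, the change score gives 0.15 SD. The adjusted comparison gives 0.255 / 0.225 / 0.195 SD at r = 0.3 / 0.5 / 0.7.

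**3. Effect on power, randomized Aim 3 comparison.** The plan states no power for this analysis, so there is no figure to reproduce. From the documents: 200 families in Aim 3 (10.1), 2:1 allocation (5.2), 10% attrition and alpha 0.05 (10.4). Then 200 × 0.9 = 180, or 120 vs 60. Assumed: e3 = 0.3 SD, share s of it present at Time 1, r = 0.3 / 0.5 / 0.7, equal SDs, a two-sided test.

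- SE of a difference in means = √(1/120 + 1/60) = 0.158 SD
- SE of the difference in change = 0.158 × √(2(1 − r)) = 0.187 / 0.158 / 0.122 SD
- Power = P(|Z + 0.3(1 − s)/SE| > 1.96), using the SE of the difference in change

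| s | Difference estimated (SD) | Power at r = 0.3 / 0.5 / 0.7 |
|---|---|---|
| 0% | 0.30 | 36 / 47.5 / 69% |
| 25% | 0.225 | 23 / 30 / 45% |
| 50% | 0.15 | 13 / 16 / 23% |

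Section 5.2 counts Aim 2 families as controls too ("For participants in the control group (Aim 2 and those randomized to control group in Aim 3), there will be no change"). With them pooled, controls number 180 + 60 = 240. The bias is the same, and power is 62 / 77 / 93%, 40 / 52 / 74% and 21 / 27 / 41% for the three rows.

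**4. Whether the trajectory plots would reveal it.** Before attrition Aim 3 has 133 vs 67. The SE of the Time 1 difference is √(1/133 + 1/67) = 0.150 SD, and the 95% half-width is 1.96 × 0.150 = 0.29 SD. Power to detect a Time 1 difference of 0.15 SD is 17%. The plots could show an early separation but could not rule one out.

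**5. Precision where Time 1 did come first, randomized comparison.** The variance factor is 2(1 − r) for change and 1 − r² for adjusted Time 3. Their ratio is (1 + r)/2 = 0.65 / 0.75 / 0.85, a reduction of 35 / 25 / 15%. The difference detectable with 80% power is 2.80 × 0.158 × √factor:

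| Analysis | r = 0.3 / 0.5 / 0.7 |
|---|---|
| Change score | 0.52 / 0.44 / 0.34 SD |
| Time 3 adjusted for Time 1 | 0.42 / 0.38 / 0.32 SD |
| Time 3 alone | 0.44 SD throughout |

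**The case against.** The second schedule in 5.2 looks like an unrevised duplicate: it repeats the first with only the timing phrase changed, and two further sections side with the first. The attachments may fix the order. The analysis is exploratory, and the cover note says the plan was simplified to primary outcomes, so it may not have been kept. The effect size, shares and correlations have no source in the documents, and with two weeks of daily messages still to come, nothing shows that a large share of any effect would be present at Time 1. A change-score t-test is valid in randomized groups when Time 1 comes first, and the covariate rule in 14.1 could admit a Time 1 score.

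Most of this stands and limits the weight of the point. It does not remove the conflict within 5.2, and choosing the before-discharge wording does not settle the order, because the education falls in the same window. The covariate rule would admit a Time 1 score only if it happened to be unbalanced between groups; baseline symptoms may already cover PCSI, but not knowledge, self-efficacy or anxiety.

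A reader might go further and infer that the plan, as written, puts the first survey after the education: footnote 29 counts a subject as enrolled "when they consent to be in the study", education is given at enrollment, and no waiting period follows consent. The documents do not support that. The footnote is form guidance on counting subjects. Section 20.4 says that consent directly precedes research procedures, and the survey is one of these. Education also requires randomization, which follows consent, so there is room for the survey in between.

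**Conclusion.** The timing conflict is real, and nothing in the text establishes that Time 1 precedes the education; either order is possible. The bias is conditional. It needs education first, an immediate shift in scores, and an analysis that was retained. Under those conditions the change comparison loses exactly the effect present at Time 1. In the randomized comparison, for the assumed 0.3 SD effect, a 25% share cuts power by about a third and a 50% share by about two thirds. These sizes are illustrative and use the planned sample; with the smaller sample mentioned on the cover, power is lower throughout. The primary outcome is untouched. Severity is minor, but the correction is cheap and also yields a more precise analysis where Time 1 came first.

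**What to change.** - **Timing.** Reconcile the second schedule in 5.2 with the first and with 5.3 and 5.4. State that the Time 1 cognition and symptom items are collected after consent and before allocation is revealed or any education is given. Items on provider communication in the ED may stay at the end of the visit. If data are already collected, report the actual order of survey and education.
- **Where Time 1 came first.** In the randomized Aim 3 comparison, replace the change-score t-test by a comparison of Time 3 scores adjusted for the same measure's Time 1 score plus the planned covariates.
- **Where education came first.** Compare Time 3 scores without Time 1.

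**Cost.** If enrollment is open: wording and question order, possibly a Time 1 survey in two short parts, with no new items or visits. If it is closed, as the cover note suggests: one sentence on the order and a choice of model on existing data. Leaving Time 1 out gives up precision: 0.44 SD is detectable, against the 0.42 / 0.38 / 0.32 SD that a clean Time 1 would have allowed.

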### 5.4. Data to be collected, including long-term follow-up data:

**Aim 1:** The goal of the parent interview will be to (1) explore their experiences with communication in the ED following their child's concussion and (2) provide critical feedback on the content and design of the CDC ACE Care Plan. The Cultural Treatment Adaptation Framework, will provide the foundation for the open-ended question guide for parents, with questions about the handout focusing on: (1) language and semantics, (2) use of culturally relevant examples, and 3) preferences for material delivery. The goal of the healthcare provider interviews will be to review the CDC ACE Care Plan handout and the RED Toolkit, and provide feedback about (1) barriers and facilitators to implementation in the ED and (2) the type of support (e.g., materials, training) that they believe would be helpful for implementation. CFIR^24 will provide the foundation for the open-ended question guide for healthcare providers, with a focus on individual characteristics (e.g., provider knowledge and self-efficacy), implementation toolkit characteristics, and aspects of the inner setting (e.g., time pressures in the busy ED, compatibility with existing communication networks and tools such as the EHR system) that may constrain implementation success.

**Aims 2 and 3:** Survey data will be collected from up to 200 parents at three time points: at initial ED visit before discharge, one day post-visit, and at 2-week follow-up. **Primary outcome.** Our primary outcome will be parenting behaviors at 2 week follow-up (emotional support and instrumental support). **Secondary outcomes.** Parent surveys at initial ED visit before discharge, one day post-visit, and two-weeks post visit will assess parent cognitions related to concussion management and proximal cognitions (concussion management knowledge and self-efficacy), parental anxiety related to concussion management, youth outcomes (health-related quality of life, post-concussion symptoms), the nature of provider-parent communication in the ED (e.g., did the parent have an opportunity to ask questions?), and additional

covariates (demographics and environmental conditions). In Aim 3 only, the parent surveys at 2 weeks post-visit will also include questions about their experiences with receiving the education toolkit.

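### The exploratory scores are compared by t-tests on change, which cannot carry the covariate adjustment promised in the same paragraph and are less precise than adjusting for each score's own Time 1 value

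*Combined protocol and SAP*

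**What the plan says.** Section 5.4 makes parenting behaviors at two weeks the primary outcome. For the secondary outcomes it says: "Parent surveys at initial ED visit before discharge, one day post-visit, and two-weeks post visit will assess parent cognitions related to concussion management". It lists anxiety and youth outcomes alongside. No schedule shows which instrument is given at which survey.

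Section 14.1 (Aims 2 and 3) sets the status of the score analyses: "We will also conduct exploratory analyses of the mean change in parent cognitions related to concussion management". Change is compared "from Time 1 to Time 3, between the groups using t-tests, and plotting trajectories for each group". The next sentence says "We will adjust analyses for child age, sex, baseline post-concussion symptoms/severity", and then extends adjustment to further covariates "if associated with outcome and distributions vary by treatment group". It is unclear whether that condition governs the whole list or only the further covariates. No regression, ANCOVA or repeated-measures model is named. Apart from baseline symptoms, no score is adjusted for its own Time 1 value.

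The timing of Time 1 is given in two ways. Sections 5.3 and 5.4, and one paragraph of 5.2, place it at the ED visit before the family leaves. A later paragraph of 5.2 says "survey data will be collected from parents at three time points: immediately post-visit, one day post-visit, and at 2-week follow-up". Section 5.2 also says "the toolkit will consist of brief education from a member of the ED study team at enrollment", without giving the order of education and first survey.

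The cover note says that the sample was smaller than planned and that the analysis was simplified to the primary outcomes.

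**The concern.** Two things are wrong with the test as written.

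First, a two-sample t-test has no place for age, sex or baseline severity. The stated test and the promised adjustment cannot both be the analysis, so the analyst would have to choose a model after seeing the data.

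Second, subtracting the Time 1 score fixes its coefficient at 1. When the two measurements are imperfectly correlated, that subtracts too much and adds noise. Estimating the coefficient is more precise in a randomised comparison and needs only data already planned.

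What is at stake is modest. Section 1.2 expects greater understanding in families who receive the toolkit, and concussion knowledge is the nearest listed measure. An imprecise comparison of that score could leave a real difference unseen, the more so in a smaller sample.

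**Working it through.** **The plan's own figure.** Section 10.4 claims at least 98% power for a 20-point difference in a reach proportion, with 200 per group and 10% attrition. With 180 per group and the least favourable base rate (40% against 60%), two-sided 5%, power is 96.9%; with 200 per group and no attrition it is 98.1%. The figure reproduces approximately, but it does not concern these scores. The documents give no effect size, SD or correlation for any of them.

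**Sample sizes.** Section 5.2 gives 2:1 allocation in Aim 3; section 10.4 gives 200 families per cohort and 10% attrition.
- Aim 3 only: 200 splits into about 133 intervention and 67 control; times 0.9, this is 120 and 60.
- Aim 2 controls pooled: 67 + 200 = 267 controls; times 0.9, this is 240, against 120.

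**Assumptions.** Equal SD at both times (set to 1), correlation ρ, a 0.4 SD effect, two-sided 5%, normal approximation. ρ and the effect are assumed.

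**Formulas.** Per-person variance:
- change score: 2(1 − ρ)
- Time 3 adjusted for own Time 1: 1 − ρ² = (1 − ρ)(1 + ρ)
- ratio, adjusted to change: (1 + ρ)/2

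Power = Φ(0.4/SE − 1.96), where SE = √(per-person variance) × √(1/n₁ + 1/n₂). The second factor is √(1/60 + 1/120) = 0.158 for Aim 3 alone and √(1/240 + 1/120) = 0.112 when pooled.

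Example, Aim 3 only, ρ = 0.5. Change score: SE = 1.000 × 0.158 = 0.158, and Φ(2.530 − 1.96) = 72%. Adjusted: SE = 0.866 × 0.158 = 0.137, and Φ(2.921 − 1.96) = 83%.

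| ρ | Variance ratio | Power, 60 v 120: change → adjusted | Power, 240 v 120: change → adjusted |
|---|---|---|---|
| 0.4 | 0.70 | 64% → 79% | 90% → 97% |
| 0.5 | 0.75 | 72% → 83% | 95% → 98.5% |
| 0.7 | 0.85 | 90% → 94% | 99.6% → 99.9% |

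The variance ratio is 0.60 at ρ = 0.2 and 0.95 at ρ = 0.9. At ρ = 0.5 the change score is exactly as precise as the Time 3 score alone, since 2(1 − 0.5) = 1; below 0.5 it is worse. At ρ = 0.5 the difference detectable with 80% power is 0.384 SD adjusted against 0.443 SD by change (60 v 120), or 0.271 against 0.313 (240 v 120). The pooled power gain is smaller because power at 0.4 SD is already near its ceiling. The pooled figures also treat the groups as if randomised, which they are not.

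**What Time 2 would add.** With complete Time 3 data it adds nothing to the Time 3 contrast. If a share f lack Time 3 but have Time 2, the variance ratio is 1 − f·R², where R² is the partial R² of Time 2 given baseline. For f = 0.10 and R² from 0.1 to 0.5 the reduction is 1% to 5%; for f = 0.30 it is 3% to 15%.

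**The case against.** The strongest reply is that these analyses are exploratory, are neither primary nor powered, and may have been dropped under the cover note. That stands, and it keeps the point minor. It does not make the paragraph consistent.

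A second reply is that the promised adjustment can be met by regressing change on group and covariates. That is true, and if the own Time 1 score is among the covariates, the group effect is identical to ANCOVA. For PCSI this may already be intended, if baseline symptoms means the Time 1 PCSI. For knowledge, anxiety, self-efficacy and PedsQL the plan does not say so, and no model is named for any score.

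Three stronger readings are tempting, and the documents do not support them:
- *Baseline is wasted.* It is not: the change score uses Time 1, only inefficiently.
- *Leaving Time 2 out of the tests is an important loss.* At the planned 10% attrition it costs at most about 5% in variance under the R² range shown. Section 5.4 also describes the surveys as a set, so it is not established that every score is measured at Time 2.
- *The plan commits to a complete-case analysis.* Section 14.1 provides for sensitivity analyses, imputation where appropriate, and a comparison of completers with those lost to follow-up. That is loosely specified, but it is not a complete-case rule.

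A last objection concerns the comparison itself. Section 5.2 counts Aim 2 families as controls. They come from a separate, non-randomised cohort, so if groups differ at Time 1, ANCOVA and change scores can answer different questions. This stands, and it limits the efficiency argument to the randomised Aim 3 families.

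**Conclusion.** The point holds as a minor, inexpensive improvement. That a t-test cannot carry the promised adjustment follows from the text alone and needs no assumption. The loss of precision holds for any ρ below 1 in the randomised Aim 3 comparison, given equal SDs; its size depends on ρ, and the power figures depend also on the assumed 0.4 SD effect. The 120 and 60 are planned numbers after attrition. The cover note reports a smaller sample without giving its size, so absolute power would be lower than shown.

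The result also requires Time 1 to precede the education. If it follows the education, Time 1 is not a true baseline, and change scores and baseline adjustment alike would remove part of the effect. The documents leave this open.

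**What to change.** 1. In section 14.1, replace the t-tests with a linear model of each Time 3 score on group, the score's own Time 1 value, child age, sex and baseline symptoms/severity (entered once where it is the same variable as the own Time 1 score). State whether the condition on further covariates applies to this list.
2. Report the Time 3 difference with its 95% confidence interval, labelled exploratory.
3. Make the randomised Aim 3 families the main comparison. If Aim 2 controls are included, add a cohort term and present that analysis separately.
4. A mixed model that also uses Time 2 is optional; it helps mainly with dropout.
5. Reconcile the descriptions of Time 1 in sections 5.2, 5.3 and 5.4, and state that it is measured before the education is delivered.

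Items 1 to 4 cost plan wording and standard software, with no new data. Item 5 costs wording only if Time 1 did precede the education. If it did not, wording cannot repair the baseline, and the report should say so.
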